8.2.7 Definitions of Deviations in Protocol Performance**Prescription Dose**

- **No Deviation:** $\geq 99\%$ of the PTV receives $\geq 93\%$ of the prescribed dose, and a contiguous volume of no more than 2cc inside PTV exceeds 20% of the prescribed dose.
- **Minor Deviation:** Deviations of this magnitude are not desirable, but are acceptable. Coverage that is equal to 93% of the prescribed dose and falls between 99% and 95% of the PTV, or a contiguous volume of no more than 2cc inside the PTV exceeds 20-25% of the prescribed dose.
- **Major Deviation:** Doses in this region are not acceptable. More than 1 cm^3 of tissue outside the PTV receives $\geq 120\%$ of the prescribed dose, or 93% of the prescribed dose

falls below 95% of the PTV, or a contiguous volume of no more than 2cc inside the PTV exceeds 25% of the prescribed dose.

Volume

- **Minor Deviation:** Margins less than specified, or field(s) 1-3 cm greater than specified.
- **Major Deviation:** Fields transect tumor or specified target volume(s), or fields are more than 3 cm greater than specified.

Critical Organ

- **Major Deviation:** The maximum dose to the spinal cord exceeds the limits in [section 8.2.6](#).

8.2.8 Quality Assurance Documentation:

Digital Submission:

Submission of treatment plans in digital format (either Dicom RT or RTOG format) is encouraged. Instructions for data submission are on the QARC Web site at [REDACTED]. Any items on the list below that are not part of the digital submission should be submitted in hard copy form.

Note: Black and white copies of color data may be submitted, provided lines are clearly labeled and the copy is legible. Otherwise, only color copies will be accepted.

- Within three days of the start of radiotherapy, the following data shall be submitted for on-treatment review.
 - a. Copies of all diagnostic materials (including diagnostic CT) and surgical reports.
 - b. Copies of treatment planning CT used in defining the target volumes.
 - c. Copies of simulator films and /or digitally reconstructed radiographs (DRRs) for each field. The GTV, CTV, PTV should be drawn on the simulator films.
 - d. Copies of verification (portal) films (or hard copy of real time portal images) for each field.
 - e. Copies of worksheets and/or printouts used for calculations of monitor units.
 - f. Color hard copy isodose distribution for the total composite dose plan in the axial, sagittal, and coronal planes, which includes the isocenter of the planning target volume.
 - g. RT-1 or IMRT Dosimetry Summary Form.
 - h. One set of orthogonal anterior/posterior and lateral films for isocenter localization for each group of concurrently treated beams. If portals being submitted contain an orthogonal set, this is sufficient.
 - i. Beam's Eye Views (BEVs) for all fields and showing the PTV and critical structures. BEV hard copies must be in color to enable reviewers to identify structures.
 - j. Dose volume histograms for the total treatment for the target volumes, lungs, heart, and spinal cord. If IMRT is used, a DVH shall also be submitted for a category of tissue called "unspecified tissue," which is defined as tissue contained within the skin, but which is not otherwise identified by containment within any other structure.
 - k. Documentation of an independent check of the calculated dose if IMRT is used.
 - l. If IMRT is used for tumors in the thoracic region, a description of the steps taken to suppress/manage motion to achieve appropriate simulation.

- Within one week of the completion of radiotherapy, the following data shall be submitted.
 - Copies of additional simulation films and verification (portal) films for any field modifications made subsequent to the initial reporting of data for on-treatment review.
 - A "RT-1 or IMRT Dosimetry Summary" form if changes have been made subsequent to submission of on-treatment data.
 - The "RT-2 Radiotherapy Total Dose Record" form.
 - A copy of the patient's radiotherapy record including the prescription, and daily and cumulative doses to all required areas and reference points.
 - Copies of calculations performed subsequent to the submission of the on-treatment data.
 - Copies of isodoses.
 - All data should be forwarded to:

[Redacted]

- Questions regarding the completion of RT-1 and RT-2 data forms, dose calculations or documentation should be directed to:

[Redacted]

- Questions regarding the radiotherapy section of this protocol, including treatment interruptions, should be directed to:

[Redacted]

OR

[Redacted]

8.2.9 Prophylactic Cranial Irradiation

- Prophylactic cranial irradiation (PCI) should be offered to all patients with a complete tumor response (CR) or near complete response (very good PR) with only residual chest abnormalities of indeterminate nature following completion of combined modality therapy. This will be determined based on the re-staging studies obtained following all four cycles of chemotherapy and thoracic irradiation. PCI should start approximately 3-6 weeks following the final cycle of chemotherapy. No concurrent chemotherapy is given with PCI. For patients with a response to therapy that is less than CR or very good PR, the use of PCI is at the investigator’s discretion.
- Treatment should be delivered with megavoltage radiation.
- The dose and fractionation scheme for PCI is 2500 cGy given in 250 cGy fractions. An RT-2 Form must be completed indicating the start and end date of treatment, fraction dose, number of fractions and total dose. This form should be mailed or faxed to QARC at the address in [section 8.2.8](#).
- The treatment field should encompass the entire cranial contents. The base of the field will extend from the supraorbital ridge, the lateral canthus of the orbit, through the tip of the mastoid process, which is 1.5-2 cm below the external auditory meatus, back to the C1-C2 vertebral interspace.

9.0 DOSE MODIFICATIONS AND MANAGEMENT OF TOXICITY

If different percentages of dose reductions for a given drug are required because of two different types of toxicities, the greater percentage dose reduction should be employed.

9.1 Hematologic Toxicity

Granulocyte or Platelet Counts for Day 1: Based on counts within 2 days of the start of each cycle, give the following:

Granulocytes/μl		Platelets/μl	Cisplatin, Carboplatin and Etoposide
$\geq 1,500$	and	$\geq 100,000$	100%
$< 1,500$	and/or	$< 100,000$	0*

* Hold protocol therapy; repeat counts twice weekly and reinstitute therapy at 100% when granulocytes $\geq 1,500$ /microliter and platelets $\geq 100,000$ /microliter. If counts do not reach these levels within 3 weeks of the next scheduled treatment, discontinue all protocol therapy.

Neutropenia or Febrile Neutropenia:

For nadir neutropenia in the absence of fever or with fever that is successfully treated by oral antibiotics, there will be no dose adjustment. Filgrastim, sargramostim, or pegfilgrastim are allowed for patients with neutropenia that delays day 1 chemotherapy by one week or more for cycles 3 and 4 (after the completion of radiation therapy). **WBC growth factors may not be used during radiation therapy.** Filgrastim, sargramostim, or pegfilgrastim may then be given after chemotherapy to prevent future treatment delays in subsequent cycles at the discretion of the treating physician (after the completion of radiation therapy). Any use of colony stimulating factors should be documented on the Remarks Addenda Form (C-260).

For chemotherapy delays of more than 7 days on any subsequent cycle of treatment, both chemotherapy drugs should be dose-reduced by 25% for all subsequent cycles of chemotherapy.

For neutropenic fever (ANC ≤ 500 /microliter and temperature ≥ 100.5) requiring intravenous antibiotics, the doses of all chemotherapy drugs should be reduced by 25% for the next cycle and all subsequent cycles.

For grade 4 nadir thrombocytopenia (platelets $\leq 25,000$), the dose of all chemotherapy drugs should be reduced by 25% from the previous dose for the next cycle and for all the subsequent cycles of chemotherapy.

9.2 Gastrointestinal Toxicity

Nausea and Vomiting

All patients should receive antiemetics to prevent nausea and vomiting. Specific antiemetic therapy is left to the discretion of the physician treating the patient (steroids and 5-HT3 antagonists should be used). If vomiting is severe, consider hospital admission and/or use of aprepitant if possible. Do not modify dose.

9.3 Hepatic Toxicity

Bilirubin	Etoposide
<1.5 x ULN	100%
1.5-3.0 x ULN	50%
>3.0 x ULN	30%

9.4 Nephrotoxicity

(based on measured or calculated creatinine clearance)

Creatinine Clearance (ml/min)	Cisplatin
≥ 70	100%
70-50	67%
< 50	0*

* If serum creatinine clearance is < 50 ml/min on day 1 of the next cycle, delay the start of that cycle for up to 2 weeks (check creatinine at least weekly). If CrCl decrease persists beyond 2 weeks, omit cisplatin for that cycle. If CrCl does not recover to ≥ 50 ml/min after 3 weeks, remove patient from protocol therapy.

9.5 Hypomagnesemia

Hypomagnesemia is not an indication for stopping therapy. Oral or parenteral magnesium supplementation is indicated for serum magnesium levels ≤ 1.5 mEq/l.

9.6 Neurologic Toxicity

Grade	Cisplatin/Carboplatin
0-1	100%
2	75%*
3	0**

* Patients with grade 2 neurotoxicity should recover to grade 1 or better prior to retreatment with this (75%) dose reduction. If grade 2 neurotoxicity recurs with 75%, drug will be given at 50% upon resolution of neurotoxicity to grade 0-1. If grade 2 neurotoxicity persists for 3 weeks, remove the patient from protocol therapy (see [section 14.2](#)).

** Discontinue drug for neurotoxicity \geq grade 3.

9.7 Ototoxicity

Remove patient from therapy for \geq grade 3 ototoxicity.

9.8 Allergic Reactions

Discontinue treatment promptly if \geq grade 3 anaphylaxis develops.

9.9 Grade 3/4 Non-Hematologic Toxicity

If a patient develops grade 3 or 4 non-hematologic toxicity not detailed above (excluding anorexia, fatigue, fever without grade 3/4 neutropenia, and alopecia), hold all therapy. Therapy can be restarted if the toxicity has resolved to \leq grade 1 by the time of the next treatment. Doses of all chemotherapy should then be reduced by 25%. If therapy is held for more than 3 weeks, remove the patient from protocol therapy.

9.10 Radiotherapy Dose Modifications for In-field Non-Hematologic Toxicities

Radiation treatment will be interrupted for grade 4 in-field toxicity and/or grade 4 neutropenia with fever.

Aggressive supportive care is encouraged throughout the course of radiotherapy. If the patient is near completion of therapy, then every attempt should be made to complete treatment despite acute toxicity. Otherwise, treatment should be restarted when the accompanying toxicity declines to \leq grade 2.

If treatment is interrupted for more than 3 weeks due to non-hematologic toxicity, remove the patient from protocol treatment.

Use the following treatment modification table for in-field non-hematologic toxicity:

In-field	CTCAE Toxicity Grade	XRT	Cisplatin/Carboplatin	Etoposide
Esophagus/pharynx (on day of treatment)	4	Hold treatment until \leq grade 2	Hold treatment until \leq grade 2	Hold treatment until \leq grade 2
Esophagus/pharynx (on day of chemo)	3	No change	Hold treatment until \leq grade 2	Hold treatment until \leq grade 2
Esophagus/pharynx (on day of chemo)	2	No change	No change	No change
Pulmonary	4	Discontinue	Hold treatment until \leq grade 2	Hold treatment until \leq grade 2
Pulmonary	3	Hold treatment until \leq grade 2	Hold treatment until \leq grade 2	Hold treatment until \leq grade 2
Skin	4	Hold treatment until \leq grade 2	Hold treatment until \leq grade 2	Hold treatment until \leq grade 2
Skin	3	No change	No change	No change

- 9.10.1** For grade 4 in-field esophagitis, radiotherapy and chemotherapy should be interrupted as detailed in the table above. Re-evaluate patient weekly.
- 9.10.2** For grade ≥ 3 esophagitis/pharyngitis, dermatitis, or other in-field radiotherapy-related toxicity, on day of chemotherapy administration during any treatment week, omit cisplatin/carboplatin and etoposide until toxicity resolves to grade ≤ 2 as detailed in the table above.
- 9.10.3** Radiotherapy should be interrupted only for grade 4 in-field toxicity and resumed when that toxicity has decreased to grade ≤ 2 as detailed in the table above. If the patient experiences esophagitis so that IV fluid support is needed, insertion of a feeding tube should be considered.
- 9.10.4** For grade 3 esophagitis, radiotherapy can be continued with pain management and IV support.

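### Section 9.10 gives conflicting instructions on radiotherapy at grade 3 lung toxicity and on chemotherapy at grade 3 skin toxicity, with no rule on which governs

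*Combined protocol and SAP*

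**What the plan says.** Section 9.10 has three layers.

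- **Opening text.** Radiotherapy is interrupted for grade 4 in-field toxicity or for grade 4 neutropenia with fever. Near the end of the course, every effort is made to finish. Otherwise "treatment should be restarted when the accompanying toxicity declines to" grade 2 or lower.
- **Table.** It is introduced by "Use the following treatment modification table for in-field non-hematologic toxicity". At pulmonary grade 3 the radiotherapy entry is "Hold treatment until \leq grade 2"; at pulmonary grade 4 radiotherapy is discontinued. At skin grade 3, radiotherapy, platinum and etoposide all continue unchanged.
- **Numbered paragraphs.** 9.10.3 reads "Radiotherapy should be interrupted only for grade 4 in-field toxicity and resumed when that toxicity has decreased to grade" 2 or lower, with no exception for any organ. 9.10.2 covers grade 3 or higher esophagitis or pharyngitis, "dermatitis, or other in-field radiotherapy-related toxicity, on day of chemotherapy administration during any treatment week, omit cisplatin/carboplatin and etoposide" until grade 2 or lower. Both paragraphs describe themselves as following the table.

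**The concern.** The table and the paragraphs purport to be the same rule, so a site may reasonably work from either. At two points they lead to opposite actions.

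The first is a safety matter: whether thoracic radiotherapy continues while a patient has grade 3 lung toxicity. It can also affect whether the course is completed, because section 9.10 removes a patient from protocol treatment once a non-hematologic interruption exceeds 3 weeks. The second decides whether a chemotherapy dose is given or omitted.

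Both current arms use the same text. Radiotherapy lasts 3 weeks in Arm A and 7 weeks in Arm B (section 8.2.2), so the period in which a hold decision can arise is longer in Arm B.

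**Working it through.** The plan gives no figure to reproduce. The check compares every table cell with the text rules.

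**Inputs, all from section 9.10.** The table has 7 organ-and-grade rows and 3 treatment columns: 7 × 3 = 21 cells. The text rules are:

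- 9.10.3: interrupt radiotherapy at grade 4 only; resume at grade 2 or lower.
- 9.10.2: omit platinum and etoposide on a chemotherapy day at grade 3 or higher; give again at grade 2 or lower.

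| Row | Radiotherapy: table / text | Both drugs: table / text |
|---|---|---|
| Esophagus grade 4 | hold / hold | hold / omit |
| Esophagus grade 3 | continue / continue | hold / omit |
| Esophagus grade 2 | continue / continue | continue / continue |
| Pulmonary grade 4 | **discontinue / hold, then resume** | hold / omit |
| Pulmonary grade 3 | **hold / continue** | hold / omit |
| Skin grade 4 | hold / hold | hold / omit |
| Skin grade 3 | continue / continue | **continue / omit** |

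Holding and omitting a drug until grade 2 or lower are treated as the same instruction.

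**Count.** Direct conflicts: 1 cell (radiotherapy, pulmonary grade 3) + 2 cells (platinum and etoposide, skin grade 3) = 3. Weaker mismatch: 1 cell (radiotherapy, pulmonary grade 4). No conflict: 21 − 3 − 1 = 17.

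**Can the entries be reconciled?**

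- *Pulmonary grade 3.* No. By limiting interruption to grade 4, 9.10.3 excludes the hold that the table requires.
- *Skin grade 3.* No. Both sources cover the same organ and grade. Restricting 9.10.2 to the day of chemotherapy does not help, because that is when the drugs are given or omitted.
- *Pulmonary grade 4.* Probably. The general sentences on resuming can be read as giving way to the specific row, although no exception is stated. This is why the cell is counted separately.

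**Does another rule decide it?**

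- The tie-break opening section 9.0, "the greater percentage dose reduction should be employed", applies when two different toxicities call for different reductions of one drug. Here one toxicity has two instructions.
- Section 9.9 begins "If a patient develops grade 3 or 4 non-hematologic toxicity not detailed above". Lung and skin toxicity are dealt with only later, in 9.10, so read literally 9.9 could reach them. It would then hold all therapy until grade 1 or lower, which matches neither the table nor the paragraphs. Section 9.10 is the more specific, so 9.9 is not counted as a further conflict.
- The instruction to use the table does not say what happens when a paragraph departs from it.

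**The case against.** The strongest reply is that the table is plainly the working source. Sites are told to use it, the paragraphs refer back to it, and a specific pulmonary row ordinarily prevails over a general sentence. If that reasoning makes pulmonary grade 4 a lesser point, it should soften pulmonary grade 3 as well. Section 9.9, read literally, also favors holding radiotherapy at grade 3.

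Part of this stands. The table was probably meant to govern, and a careful reader would then hold radiotherapy, which is the cautious course. But the two lung cells are not alike. At grade 4 the text is silent about an exception; at grade 3 it restricts interruption to grade 4 and so forbids what the table orders. A paragraph that claims to follow the table also gives its reader no cause to look for a difference. For skin the specificity argument is unavailable, since 9.10.2 names dermatitis.

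The reply is also right that the cell count measures disagreement in wording, not clinical impact, and that it tests only 9.10.2 and 9.10.3. Section 1.4 offers only indirect evidence on frequency. Grade 3/4 dyspnea ran from about 4% to 11% across the listed high-dose daily trials, nearly all in non-small cell disease, and no grade 3 or higher pulmonary toxicity was seen in CALGB 8837. These are poor proxies for in-field lung toxicity here and are not converted into a patient count.

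Finally, there are safeguards. Section 8.2.8 provides that "Questions regarding the radiotherapy section of this protocol, including treatment interruptions, should be directed to" a named contact. Section 8.0 gives a route for treatment questions, section 14.2 ends protocol therapy that is harming the patient, and under section 15.4 the DSMB reviews toxicity twice a year. These limit the harm without correcting the text, and a site that has read only one version has no reason to ask.

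**Conclusion.** The concern holds, with high confidence. Section 9.10 is wrong as written at three cells: radiotherapy at pulmonary grade 3, and platinum and etoposide at skin grade 3. Radiotherapy at pulmonary grade 4 is a lesser mismatch. The importance rests mainly on the pulmonary grade 3 conflict, because it bears on patient safety.

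The conclusion rests on the current wording alone; the table rows and paragraphs are complete, so the mismatch is not an artifact of text extraction. How often patients reach these cells is unknown. No consequence for power, type I error or the primary analysis is claimed. This should be corrected, but it does not call the design into question.

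**What to change.** 1. Amend 9.10.3 and the opening text of 9.10 to except pulmonary toxicity in line with the table: hold radiotherapy at grade 3 until grade 2 or lower, and discontinue it at grade 4. The clinical leads should confirm this.
2. Have the clinical leads choose one chemotherapy instruction for grade 3 dermatitis and put it in both 9.10.2 and the skin row.
3. Only then add a sentence that the table governs any remaining difference. Added alone, it would settle the skin question by default instead of by clinical judgment.
4. Notify sites.

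The cost is a short protocol amendment and a site notice. Data collection, sample size and analysis do not change.

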9.11 Dose Modifications for Obese Patients

There is no clearly documented adverse impact of treatment of obese patients when dosing is performed according to actual body weight. Therefore, **all dosing is to be determined solely by (1) the patient's BSA as calculated from actual weight or (2) actual weight without any modification unless explicitly described in the protocol.** This will eliminate the risk of calculation error and the possible introduction of variability in dose administration. **Failure to use actual body weight in the calculation of drug dosages will be considered a major protocol deviation.** Physicians who are uncomfortable with administering chemotherapy dose based on actual body weight should not enroll obese patients on Alliance protocols.

10.0 COMPANION STUDIES

There are two substudies within CALGB 30610. Patients who receive one cycle of chemotherapy prior to registering on CALGB 30610 will NOT be offered participation in either companion study.

The correlative science and the quality of life studies must be offered to all patients enrolled on CALGB 30610 (although patients may opt to not participate). These substudies do not require separate IRB approval. The substudies included within CALGB 30610 are:

- CALGB 150712: Correlative Science Studies in CALGB 30610
- CALGB 70702: Quality of Life Studies in CALGB 30610, **closed to accrual as of 8/30/17**

10.1 Correlative Science Substudies (CALGB 150712)

10.1.1 Exploratory Investigation of Circulating Biomarkers

The goal of the first correlative study is to use the multiplex bead assay to systematically examine potential blood-based biomarkers of anti-tumor response and therapeutic resistance to the two chemoradiotherapy regimens, with a focus on circulating cytokines and angiogenic factors.

This correlative study will be performed at MD Anderson Cancer Center in the laboratory of [REDACTED]

Rationale: Previous studies have established that both the tumor response to radiotherapy and radiation-induced gastrointestinal toxicity are dependent on the induction of tumor endothelial apoptosis and angiogenesis [27, 28]. Furthermore, radiation induces compensatory pathways, including hypoxia inducible factor-1 (HIF-1), which affect endothelial survival and tumor radiosensitivity through mediators such as VEGF and basic

FGF [29]. Interestingly, the sequencing and frequency of radiotherapy had a significant impact on the activation of these pathways [29]. Assessing the treatment-induced changes in circulating angiogenic factors and cytokine expression, particularly HIF-regulated factors, may therefore provide important information regarding the tumor response to different treatment regimens. In this study we will investigate a biomarker profile consisting of circulating potential blood-based biomarkers of response and resistance, including proangiogenic cytokines (i.e., EGF, bFGF, IL-8) and markers of endothelial damage (soluble E-selectin, soluble VEGFR-2).

Objectives: The exploratory objectives of the correlative study are:

1. To determine whether the baseline biomarker profile, or changes in the profile during treatment, correlate with clinical outcome as judged by objective response rate, progression free survival, and overall survival.
2. To compare the changes in the biomarker profile between the two treatment arms.

Hypotheses

1. Higher-dose, accelerated radiation therapy will cause a larger rise in circulating markers of endothelial damage than hyperfractionated and accelerated radiotherapy (HFXART) due to a greater induction of tumor endothelial apoptosis.
2. Other circulating biomarkers may be useful for helping to identify patients most likely to benefit from therapy, monitor antitumor responses, and understand mechanisms of therapeutic resistance.

Method for Multiplex Bead Assay

Plasma will be used for the assay. We will use the multiplexed bead suspension arrays for 33 C/AFs (Biosource™ Human Cytokine 30-Plex for Luminex™ panel, Biosource, Camarillo, CA; Lincoplex™ Human Cardiovascular Disease I kit, LINCO Research/Millipore, St. Charles, MO). The Luminex Multiplex Cytometric Bead Array (Multiplex) assay is ideal for exploratory investigations using statistical support. The assay has many advantages. It requires as little as 50 µl of plasma, rather than the 100-200 µl that is required for the routine ELISA procedures. In addition, the Multiplex has an advantage over the ELISA in its ability to measure up to 25-33 cytokines in one run using a single sample, thereby providing relative concentrations among 25-33 cytokines and also minimizing the variance of the data.

